- POH Supplies, Capital Equipment, Facilities, and Other costs: we will consider POH Supplies, Capital Equipment, Facilities, and Other costs on a per participant and/or per meal basis.

Intervention A – Navigation (costs will only apply to participants randomized to these groups):

- Staff (health system): we will ask staff to record or estimate the time it takes to:
 - Schedule session with participant
 - Prepare for session with participant
 - Engage in session with participant

- Complete follow-up tasks from session with participant
- Hand off to POH
- Staff (POH): we will estimate the time it takes for staff to:
 - Receive hand off from health system
 - Schedule session with participant
 - Prepare for session with participant
 - Engage in session with participant
 - Complete follow-up tasks from session with participant
- Participant: we will estimate participant time from the reported staff time for scheduling and engaging with participant.
- Supplies, Capital Equipment, Facilities, and Other costs: we will estimate overhead costs based on staff time per participant.

Intervention B – Text Messaging (costs will only apply to participants randomized to these groups):

- Staff (health system):
 - Time to draft text messages
 - Time to program messages into Eureka
- Cost of delivering messages through Twilio, the service used by Eureka
- Participants will report monthly cost of phone service, include text messaging on the Time and Costs questionnaire.

Data Collection, Retention, and Monitoring

Data for Phase 1 will be recorded in study records on UCSF REDCap or UCSF OneDrive.

The primary data collection source for Phase 2 will be the Eureka Research Platform. This platform includes participant-facing interfaces for data collection, along with investigator- and clinical research staff-facing interfaces for data entry and management.

Participant data for Phase 2 will also be collected from the UCSF Electronic Health Record and entered in the Eureka Research Platform.

Data Collection Instruments

The Investigator will prepare and maintain adequate and accurate source documents designed to record all observations and other pertinent data for each participant.

Where possible, the participant will be asked to supply information regarding participant-oriented outcomes via participant questionnaires in the Eureka Research Platform. If participants are not able to enter their own responses, study staff may enter participant responses through proxy data entry by interviewing the patient in-person or over phone or video.

Study personnel will enter data from source documents corresponding to a participant's visit or participant events into the study Eureka database when the information corresponding to that visit or event is available.

The Investigator is responsible for all information collected on participants enrolled in this study. All data collected during the course of this study must be reviewed and verified for completeness and accuracy by the Investigator.

[Data Management Procedures](#)

The data will be entered into the Eureka database. Database lock will occur once quality assurance procedures have been completed. All procedures for the handling and analysis of data will be conducted using good statistical and computing practices.

[Data Quality Control and Reporting](#)

After data have been entered into the study database, a system of computerized data validation checks will be implemented and applied to the database on a regular basis. The study database will be updated in accordance with the resolved queries. All changes to the study database will be documented.

[Archival of Data](#)

The database is safeguarded against unauthorized access by established security procedures, including two-factor authentication for investigator and study staff access; appropriate backup copies of the database and related software files will be maintained. Databases are backed up by the database administrator in conjunction with any updates or changes to the database. At critical junctures of the protocol (e.g., production of interim reports and final reports), data for analysis is locked and cleaned per established procedures.

[Availability and Retention of Investigational Records](#)

The Investigator must make study data accessible to authorized representatives of the Funder (or designee), IRB/IEC, and Regulatory Agency (e.g., FDA) inspectors upon request. A file for each participant must be maintained that includes the signed Informed Consent, HIPAA Authorization and Assent Form and copies of all source documentation related to that participant. The Investigator must ensure the reliability and availability of source documents from which the information in the study database was derived.

All study documents (patient files, signed informed consent forms, Study File Notebook, etc.) must be kept secured for a period of two years following the conclusion of the study.

[Monitoring](#)

Monitoring visits may be conducted by the Funder (or designee), UCSF, or other regulatory bodies (e.g., IRB, FDA).

Participant Confidentiality

In order to maintain participant confidentiality, all participants will be assigned a unique participant number. That number will be used to identify the participant on all study materials.

Data Sharing

Participant data will be shared with Project Open Hand so that Project Open Hand can provide services to the participants.

The UCSF Coordinating Center will be responsible for creating analytic datasets for study investigators. Data generated within this study will be provided to the American Heart Association in a de-identified form, to be deposited within the Health Care x Food data repository on the Precision Medicine Platform, and subject to the Precision Medicine Platform Terms and Conditions. Data on the Precision Medicine Platform will be collated with data from other studies that are funded by the American Heart Association Health Care x Food initiative, and used by future investigators for analysis. In addition, data will be made available on Dryad, in alignment with agreed-upon Open Science Policies at the American Heart Association, whereby any factual data that is needed for independent verification of research results must be made freely and publicly available in an AHA-approved repository as soon as possible, and no later than the time of an associated publication or the end of the award period (and any no-cost extension), whichever come first.

Administrative, Ethical, and Regular Considerations

The study will be conducted according to the Declaration of Helsinki, Protection of Human Volunteers (21 CFR 50), Institutional Review Boards (21 CFR 56), and Obligations of Clinical Investigators (21 CFR 312).

To maintain confidentiality, all records will be identified by a coded number only. All study records will be kept in a secure electronic file or locked file cabinet and code sheets linking a patient's name to a patient identification number will be stored separately in another secure electronic file or locked file cabinet. Clinical information will not be released without written permission of the participant, except as necessary for monitoring by the FDA. The Investigator must also comply with all applicable privacy regulations (e.g., Health Insurance Portability and Accountability Act of 1996, EU Data Protection Directive 95/46/EC).

Protocol Amendments

Any amendment to the protocol will be written by the Principal Investigator. Protocol amendments cannot be implemented without prior written IRB/IEC approval except as necessary to eliminate immediate safety hazards to patients. A protocol amendment intended to eliminate an apparent immediate hazard to patients may be implemented immediately, provided the IRBs are notified within five working days.

Institutional Review Boards and Independent Ethics Committees

The protocol and consent form will be reviewed and approved by the IRB/IEC prior to study initiation. Serious adverse experiences regardless of causality will be reported to the IRB/IEC in accordance with the standard operating procedures and policies of the IRB/IEC, and the Investigator will keep the IRB/IEC informed as to the progress of the study. The Investigator will obtain assurance of IRB/IEC compliance with regulations.

Any documents that the IRB/IEC may need to fulfill its responsibilities (such as protocol, protocol amendments, Investigator's Brochure, consent forms, information concerning patient recruitment, payment or compensation procedures, or other pertinent information) will be submitted to the IRB/IEC. The IRB/IECs written unconditional approval of the study protocol and the informed consent form will be in the possession of the Investigator before the study is initiated. This approval must refer to the study by exact protocol title and number and should identify the documents reviewed and the date of review.

Protocol and/or informed consent modifications or changes may not be initiated without prior written IRB/IEC approval except when necessary to eliminate immediate hazards to the patients or when the change(s) involves only logistical or administrative aspects of the study. Such modifications will be submitted to the IRB/IEC and written verification that the modification was submitted and subsequently approved should be obtained.

The IRB/IEC must be informed of revisions to other documents originally submitted for review; serious and/or unexpected adverse experiences occurring during the study in accordance with the standard operating procedures and policies of the IRB; new information that may affect adversely the safety of the patients of the conduct of the study; an annual update and/or request for re-approval; and when the study has been completed.

Informed Consent

Informed consent will be obtained in accordance with the Declaration of Helsinki, ICH GCP, US Code of Federal Regulations for Protection of Human Subjects (21 CFR 50.25[a,b], CFR 50.27, and CFR Part 56, Subpart A), the Health Insurance Portability and Accountability Act (HIPAA, if applicable), and local regulations.

For Phase 1, we will obtain written informed consent via DocuSign.

For Phase 2, we will obtain eConsent via Eureka.

The Investigator will prepare the informed consent form prior to submission to the IRB/IEC. The consent form generated by the Investigator must be approved by the IRB/IEC. The written consent document will embody the elements of informed consent as described in the International Conference on Harmonisation and will also comply with local regulations. The Investigator will send an IRB/IEC-approved copy of the Informed Consent Form to the Funder (or designee) for the study file.

A properly executed, written, informed consent will be obtained from each participant prior to entering the participant into the study. Information should be given in both oral and written form and participants must be given ample opportunity to inquire about details of the study. If appropriate and required by the local IRB/IEC. A copy of the signed consent form (and assent) will be given to the participant and the original will be maintained with the participant's records.

Role of the Sponsor

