Patient Health Questionnaire – 9 ⁴⁵	Validated measure of depressive symptoms	EHR	x	x
General Anxiety Disorder - 7 ⁴⁶	Validated measure of anxiety symptoms	EHR	x	x
Tobacco use	Important CV risk factor in Life's Essential 8.	Eureka	x	x
Sleep hours	Important CV risk factor in Life's Essential 8.	Eureka	x	x
Blood pressure	Important CV risk factor in Life's Essential 8.	EHR	x	x
Weight/Body Mass Index (BMI)	Important CV risk factor in Life's Essential 8.	EHR	x	x
Cholesterol	Important CV risk factor in Life's Essential 8.	EHR	x	x
Hemoglobin A1c	Important CV risk factor in Life's Essential 8.	EHR	x	x
Self-reported minutes/week of moderate to vigorous physical activity	Important CV risk factor in Life's Essential 8.	Eureka	x	x
Steps/day	Objective measure of physical activity in people with available data.	Eureka	x	x
Six-minute walk distance ⁴⁷	Objective exercise capacity measure collected routinely as an outcome in CR programs.	EHR	x	x
Satisfaction with the intervention(s) ⁴⁸	Measure of acceptability.	Eureka		x
Net promoter score	Measure of acceptability	Eureka		x
Time and costs	Custom questionnaire to help estimate costs.	Eureka		x
Consumption of food	Custom questionnaire to report consumption of distributed food	Eureka		x
Cardiovascular Events	Events include CV hospitalizations for myocardial infarction, heart failure, stroke, and deaths.	EHR		x
Number of CR sessions attended	Attending a greater number of CR sessions is associated with greater benefit. ⁴⁹	EHR		x
Number of FIM meal units	Primary outcome of study. We will be able to determine this outcome in all participants. Because some participants will receive groceries and some participants will receive meals, we will define this outcome as a meal "unit" received from POH. A meal unit is defined as 7 packaged meals (delivery), 1 grocery box (delivery), 1 set (5 or 7) of packaged meals (pick-up), or 1 grocery distribution (pick-up). We will collect number of FIM meal units throughout participants' 3-month study participation and throughout their insurance authorization period.	POH		x

	We will also collect number of FIM meal units for their dependents, if applicable.			
--	--	--	--	--

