We will conduct optional individual semi-structured interviews in a convenience sample of study participants and staff with regard to implementation of the interventions. Participants will be asked to provide verbal consent for the interviews. Interviews will be audio-recorded and transcribed without reference to the participant identify.

Phase 2 Participant Compensation

Participants will receive \$50 for completing eVisit 1 (Month 0) and \$50 for completing eVisit 2 (Month 3) and \$50 for completing the optional interview.

Comparators

Intervention A: Navigation: Navigation will occur at both the health system and FIM program levels. The health system navigator will be separate personnel from CR program staff to limit effects on usual care. Navigation will include: motivational interviewing,²⁴ patient-determined visits (i.e., phone, video, or in-person visits depending on patient preference), and delivery of a structured approach to participation: 1) explain the program, 2) explain the benefits, 3) provide positive endorsement, 4) describe process to enroll, 5) welcome questions, 6) address barriers to attendance, and 7) provide with follow-up information.²³ Health system navigation will include at least 3 attempts to contact participant for each individual session. Participants will have 1 weekly navigation session until the participant enrolls in the FIM program or declines further contact. Scripts will be refined based on Phase 1 activities. FIM program navigation will include individual in-person, video, or telephone contacts by FIM staff to participants to address participation barriers. FIM navigation contacts will occur on a weekly basis until the participant has achieved sufficient engagement (receipt of 8 FIM meals) or the participant declines further contact. Scripts will be refined based on Phase 1 activities.

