Intervention B: Text-messaging: The text-messaging intervention will be informed by behavioral science.³² Text messages will promote healthy eating and participation in a FIM program through behavior change techniques: provide information about behavior-health link (“Did you know that joining a Food is Medicine program like Project Open Hand can lower your chance of being hospitalized?”), provide instruction (“When cooking, use olive oil or canola oil instead of butter”), prompt intention formation (“Write a list of 3 reasons you want to eat healthy foods, and put the list somewhere you will see it often”), and provide general encouragement (“Did you eat a heart-healthy meal today? ”)³² The initial text messaging library will be adapted from messages found acceptable in our previous research. Text messaging will be refined in Aim 1. Text messages will be tailored based on a programmed algorithm (e.g., before initiating the FIM program will receive messages about enrolling and after initiating the program will receive messages about engagement). Participants will receive 2-4 text messages per week (frequency to be determined in Aim 1)²⁸ until the end of the 3-month intervention or until the participant opts out of text messages.

Usual Care: All participants will receive a MyChart message with written instructions about how to enroll in a Food is Medicine program.

Adverse Experience Reporting and Documentation

For this minimal risk study, the risks related to participation in the research are related to the potential loss of privacy due to participation in research and potential discomfort related to sensitive questions on questionnaires. However, we recognize that this population may experience adverse events due to their underlying health conditions, and that reporting of these adverse events may be relevant to understanding the effects of the interventions and Food is Medicine programs more broadly. Thus, we plan to collect data on adverse events as part of this study.

Adverse Events

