A protocol violation occurs when the participant or investigator team fails to adhere to significant protocol requirements affecting the inclusion, exclusion, subject safety and primary endpoint criteria.

When a protocol violation occurs, it will be discussed with the investigator and a Protocol Violation Form detailing the violation will be generated. This form will be signed by the Investigator. A copy of the form will be filed in the site's regulatory binder.

Data Safety Monitoring

This minimal risk study will not have an external Data Safety Monitoring Board. The Principal Investigator will monitor study data for completeness and monitor and report adverse events as described above.

Analysis Methods

Phase 1: We will qualitatively describe participant responses using rapid template analysis³⁵ based on the Theory of Planned Behavior³⁶ and emergent themes. At least two study staff members will review and code transcripts. Study staff members will meet to achieve consensus, with any disputes resolved by the Principal Investigator.

Phase 2: Respecting statistical norms for pilot studies, the proposed pilot randomized trial mimics the design we hope to use in the future and does not provide p-values or formal sample size calculations.⁵¹ The pilot study will provide information on the acceptability of the interventions. The sample size represents 1/3 of CR patients seen at UCSF in 9 months.

With a sample size of 42 for each experimental condition, this pilot study would be able to estimate a mean satisfaction score of 3.5 (scale of 1 to 5, with 5 being very satisfied) with a 95% confidence interval from 3.2-3.8, assuming a standard deviation of 1.

This pilot study will address two hypotheses (N=42 each) for the secondary outcome (which we expect to be the primary outcome for the future larger study):

Hypothesis A: Navigation + UC (\pm text messaging) [experimental] will result in a greater mean number of FIM meals received in 3 months than UC (\pm text messaging) [control].

Hypothesis B: Text messaging + UC (\pm navigation) [experimental] will result in a greater mean number of FIM meals received in 3 months than UC (\pm navigation) [control].

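### How adverse events are found is not defined and could differ by navigation arm; separately, cardiovascular events taken only from the EHR may be undercounted in every arm

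*Combined protocol and SAP*

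**What the plan says.** The section Adverse Experience Reporting and Documentation classes the study as minimal risk, then gives a reason for collecting adverse events: "reporting of these adverse events may be relevant to understanding the effects of the interventions". It concludes: "Thus, we plan to collect data on adverse events as part of this study". Events are to be entered in Eureka with dates, severity, outcome, treatment and relatedness. All SAEs are to be documented, related or not, from consent until the final visit is complete.

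Table 2 lists what is measured at months 0 and 3. It has no item asking participants about adverse events, admissions or emergency visits. Its one event row is cardiovascular events, source EHR, month 3: "Events include CV hospitalizations for myocardial infarction, heart failure, stroke, and deaths". The number of these events in 3 months is a secondary endpoint.

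Under Comparators, health-system navigation is weekly until the participant enrols in the FIM program or declines. For the FIM program, "FIM navigation contacts will occur on a weekly basis until the participant has achieved sufficient engagement", defined as 8 FIM meals, or until the participant declines. Under Phase 2 Blinding, staff who deliver navigation know that allocation. The contacts scheduled for every participant are two eVisits.

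Under Data Collection, Retention, and Monitoring: "Participant data for Phase 2 will also be collected from the UCSF Electronic Health Record". No other health record is named, while the inclusion criteria admit patients from UCSF or ZSFG.

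**The concern.** An AE count depends on how often events happen and on how likely they are to be heard of. The protocol fixes where events are stored but not how they come to light. Many of the events it expects, such as fatigue, heartburn or sore muscles, may never reach a chart and would surface only if a participant mentions them to staff. The scheduled opportunity to do so is greater with navigation than without. If AEs are then summarised by arm, as the stated purpose invites, a difference in reporting could be read as an effect of navigation.

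The CV endpoint raises a different question. Its source is the same in all arms, so what matters is completeness: admissions at ZSFG or elsewhere may be absent from the record that is abstracted. With few events expected, losing even one or two matters to what can be described.

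**Working it through.** **The plan's own figure.** The only design calculation concerns satisfaction: "With a sample size of 42 for each experimental condition", a mean of 3.5 is estimated "with a 95% confidence interval from 3.2-3.8, assuming a standard deviation of 1". Check: 3.5 ± 1.96 × 1/√42 = 3.5 ± 0.302, or 3.198 to 3.802 (with the t distribution on 41 df, 3.188 to 3.812). Both round to 3.2 to 3.8, so the figure is reproduced. The documents give no figure for AEs or CV events.

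**Inputs.** From the documents: 84 participants, 42 with and 42 without each intervention, 21 per cell. Not in the documents, therefore assumed: true AE risk 0.4 (range 0.2 to 0.6); AE detection 0.9 with navigation and 0.5 to 0.9 without; CV event risk 0.05 (range 0.02 to 0.10); EHR capture 0.6 to 1.0.

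**Adverse events, no true effect of navigation.** Expected number recorded = 42 × risk × detection.

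| Detection with / without navigation | Recorded with / without | Apparent ratio |
|---|---|---|
| 0.9 / 0.9 | 15.1 / 15.1 | 1.00 |
| 0.9 / 0.7 | 15.1 / 11.8 | 1.29 |
| 0.9 / 0.5 | 15.1 / 8.4 | 1.80 |

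The true risk cancels, so the ratio is the same at any risk from 0.2 to 0.6.

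**Text-messaging comparison.** Each side has 21 participants with navigation and 21 without. At detection 0.9 and 0.5, each side expects 21 × 0.4 × 0.9 + 21 × 0.4 × 0.5 = 11.8 recorded events, a ratio of 1.00. The problem is confined to the navigation comparison.

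**Cardiovascular events.** With capture s equal in both groups, the observed ratio is (s × risk 1)/(s × risk 2), and s cancels. A true ratio of 0.5 stays 0.5. Counts do fall. At 5% risk, 84 × 0.05 = 4.2 events are expected:

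| Capture | Missed of 4.2 | Expected per 42 | Chance of no events in 42 |
|---|---|---|---|
| 100% | 0 | 2.1 | 0.95^42 = 12% |
| 80% | 0.8 | 1.7 | 0.96^42 = 18% |
| 60% | 1.7 | 1.3 | 0.97^42 = 28% |

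At 2% risk, 0.3 to 0.7 of 1.7 expected events are missed; at 10%, 1.7 to 3.4 of 8.4.

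**The case against.** A reader might infer that navigation arms will show more AEs and SAEs, and that the CV comparison is biased as well. The documents support neither.

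- Nothing says that navigators ask about or record health events. Their listed tasks concern the program, its benefits, enrolment and barriers.
- Navigation contact can end early, and the other arms are not without contact: Cost Estimation includes intake and continuing engagement by POH staff under usual care.
- The EHR review covers all arms and looks for CV admissions and deaths, so those SAEs have a common source. Assuming detection of 0.8 against 0.2 to 0.4 would give a 2- to 4-fold excess, but those rates have no basis in the documents and make no allowance for that source.
- For CV events, unequal staff contact does not enter the count unless navigator reports are added to it.
- No between-arm AE analysis is planned. This is a minimal-risk pilot that "does not provide p-values or formal sample size calculations".
- The documents do not say whether ZSFG or outside records can be viewed, and AEs might be captured on a Eureka form not listed in Table 2.

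These points limit the concern but do not remove it. If navigators learn of an admission, the commitment to document all SAEs obliges the study to record it. If they record nothing, no stated route exists for most AEs. Either way, the method of ascertainment needs stating. Analysis Methods also says the pilot mimics the intended future trial, so the gap could carry forward.

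**Conclusion.** The point holds in limited form. AE and SAE ascertainment is undefined, and the design gives navigation participants more scheduled chances to report. Differential recording is therefore a risk, not an established bias. The apparent ratio of 1.3 to 1.8 illustrates that risk under assumed detection rates; it does not estimate it. The risk bears on descriptive safety data for navigation against no navigation.

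The CV endpoint may be incomplete in every arm. The consequence is fewer events and less precision, with no expected distortion of the ratio as long as the EHR remains the only source and is searched alike in all arms. The loss of about 0.8 to 1.7 events depends on the assumed 5% risk and 60 to 80% capture. The primary endpoint and the meal outcome are unaffected.

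**What to change.** 1. Add to Table 2 one fixed item, source Eureka, month 3, identical in all arms, on hospital admissions and emergency visits since randomisation.
2. Use positive answers to prompt confirmation of SAEs, and of CV events treated outside the abstracted EHR.
3. State that ZSFG records are searched as well as UCSF's.
4. Base any AE or SAE summary by arm on this item plus the EHR review, and list separately the events learned only through navigation contacts.

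With equal detection, the apparent AE ratio under no true effect returns to 1.00.

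The cost is about a minute of participant time in an eVisit that already exists, and some records to confirm. Participants who do not complete eVisit 2 will give no self-report, so the number completing it should be shown by arm beside the event table. The item is best kept to admissions and emergency visits. An open question on any new or worse health problem would draw many reports of symptoms the protocol calls common in this population, each needing dates, severity and relatedness.
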